17.5 Subgroup analyses

Pre-specified subgroup analyses will be carried out by including a treatment group by subgroup interaction parameter in the regression model and reporting adjusted treatment effects with 95% confidence intervals. Results of subgroup analyses will be interpreted cautiously. Subgroups will be detailed in the SAP and will include baseline factors such as country and facility size, as well as subgroups defined during the intervention phase such as high and low intervention fidelity.

APT-Sepsis Protocol (Uganda) V3.007/11/2024

18 **HEALTH ECONOMICS**

The objective of the economic evaluation is to compare the cost-effectiveness of APT-Sepsis against usual care. This will be done from the healthcare provider perspective.

We will perform a cost-consequence analysis in the first instance, based on costs and outcome for both trial arms and presented in a disaggregated summary format on the cost-effectiveness plane. We will use bootstrapping to derive cost-effectiveness acceptability frontiers. The distribution of costs and outcomes and missing data, censoring and correlations between costs and outcomes will be explored. Multiple imputation will be used for missing data.

We will explore the extent to which is feasible or appropriate to conduct an incremental cost effectiveness analysis presented in terms of cost per QALYs using WHO weightings. Deterministic and probabilistic sensitivity analyses will be undertaken to explore the robustness of the findings to plausible variations in key assumptions and analytical methods used, and to consider the broader issue of generalisability of the study's results.

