16.2 Original sample size calculation

To this end, we have assumed an ICC of 0.03 but considered sensitivity across the range 0.001 to 0.05. We have assumed a CAC of 0.97 but considered sensitivity across the range 0.9 to 1.0. Each health facility will have a minimum of 1,500 births each year, so each health facility will contribute 2,875 (=1,500*23/12) births to the analysis (750 during the baseline phase and 2,125 post randomisation). Assuming 60 health facilities, the total sample size will be 172,500. Using methods to calculate the sample size in a parallel CRT with a baseline period previously described [6, 8] this will give over 95% power (at 5% significance) to detect a 25% relative reduction in the composite primary outcome from 3% to 2.25% after adjusting for clustering through the ICC and CAC for our base case scenario. The ICC and CAC ranges were considered through sensitivity analysis, and the study has at least 80% power in most likely scenarios. Our calculations have not allowed for varying cluster size, but our allocation process will balance on cluster size to ensure total cluster sizes are similar across the two arms of the study (see Section 12).

To allow for the possibility of health facilities dropping out, we will recruit an extra two facilities per country. It is anticipated that drop out is most likely to happen during the baseline period, in which case, these facilities will not be randomised or included in the final analysis.

17 Study Framework

The overall objectives of the primary and secondary outcomes is to test superiority of the APT-Sepsis programme compared to usual care with passive guideline dissemination

18 Timing and Objectives of Analyses

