25.2 Final Analysis

25.2.1 Levels of significance and multiplicity

All applicable statistical tests will be two-sided and will be performed using a 5% significance level; confidence intervals presented will be 95%.

There will be no adjustment for multiplicity. However, results from secondary outcomes will be considered as exploratory and results will be interpreted with caution.

Analyses will be conducted with all clusters assigned to the group they were assigned at randomisation. All observations from randomised facilities (excluding observations from the transition phase) will be included in the analysis.

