25.2.2.2 Analysis

Summary statistics of the number and percentage who experienced the outcome will be presented by trial arm, country and time-period. The denominator for the percentage calculation will be the number of live births recorded in the facility in the time period.

Outcome rates over time will be presented in a line graph, split by intervention vs control, with prerandomisation, transition and post-randomisation phases marked. Time will be anchored around date of allocation to the transition phase for each facility.

The primary analysis will use a mixed effects logistic regression models with robust standard errors. A small sample correction will not be used as there are over 40 clusters [8] The model will incorporate a constrained baseline analysis [9], where both pre-randomisation and post-randomisation time points are included as outcomes, but with the treatment effect assumed to be zero in the pre-randomisation phase. This will be implemented using two binary covariates, one indicating period (0= pre-randomisation, 1=post-randomisation), and one indicating exposure to the intervention (taking the value 0 for all clusters in the pre-randomisation period, and control clusters in the post-randomisation period, and the value 1 for the intervention clusters in the post-randomisation period). Facility and facility by period will be included as random effects, with country, and the categorical minimisation factor facility size included as covariates. The second minimisation factor (proportion of births with the composite primary outcome) is not included as proportion of births is already in the model as the outcome variable. Relative risk and risk differences will be derived using marginal standardisation, as in Kirkwood et al [10]. Under this approach, the mean risk under the control condition and intervention condition is obtained. The risk ratio is then derived using the mean risk in intervention condition and by the mean risk in the control condition, with the calculation being performed on the log scale. The risk difference is derived as the mean risk in intervention condition minus the mean risk in the control condition. We will use the unconditional standard errors to obtain the confidence interval, as this allows for correlation amongst the observations. Point estimates, 95% confidence intervals and exact p-Values will be reported. Estimation of the relative risks and risk differences, and their standard errors and confidence intervals

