will be carried out using the 'margins' command in Stata, as this method has not been implemented in SAS.

If the full mixed effects model fails to converge, we will follow the sequence of analyses:

- 1. Remove the random facility by period effect and fit a mixed effects model with random effect for facility only.
- 2. If this model also fails to converge, we will perform a cluster level analysis weighted by cluster size, calculating a cluster-level summary statistic for the pre-randomisation period and post randomisation period separately.

Queries will be raised where daily reporting of aggregate data appear to be inconsistent within care areas (e.g. a care area has reported births on one day but not the next) or where days with reporting are missing within the week.

Covariate data (country and facility size) will be complete. Country is known for each cluster and facility size is based on the number of births per cluster per week in the pre-randomisation phase.

Additional analysis

Subgroup analyses will be carried out by including a treatment group by subgroup interaction parameter in the regression model and reporting adjusted treatment effects with 95% confidence intervals. Treatment effects will be compared between subgroups using ratios of ratios using post-estimation commands. Results of subgroup analyses will be interpreted cautiously. Subgroups will include country, facility size and month of post intervention roll-out period.

Intracluster correlation coefficients and cluster autocorrelation

Estimates of ICC and CAC will be calculated on the proportion scale by fitting multilevel linear models to the binary data. Within-period ICCs for the pre-randomisation and post-randomisation periods, and between period CAC will be reported.

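### The subgroup models need subgroup-specific time terms: with one common pre/post effect, differing background change by country or facility size is read as effect modification, and the month model is under-specified

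*SAP*

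**What the plan says.** SAP 25.2.2.2 represents time in the primary model by two binary covariates, "one indicating period (0= pre-randomisation, 1=post-randomisation), and one indicating exposure to the intervention". Exposure equals 1 only for intervention facilities after randomisation. Facility and facility-by-period are random effects; country and size class enter as covariates that do not change over time.

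Under 'Additional analysis' the same section states: "Subgroup analyses will be carried out by including a treatment group by subgroup interaction parameter in the regression model". It then lists the subgroups: "Subgroups will include country, facility size and month of post intervention roll-out period". It adds: "Treatment effects will be compared between subgroups using ratios of ratios using post-estimation commands". Protocol 17.5 uses the same construction: "Pre-specified subgroup analyses will be carried out by including a treatment group by subgroup interaction parameter in the regression model".

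Neither document mentions a month main effect, a period-by-country term or a period-by-size term, and neither excludes them. Neither says whether 'treatment group' means the allocated arm or the time-varying exposure indicator. Month of roll-out has no value for baseline records, which are in the model, and no coding is given for them.

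**The concern.** A subgroup analysis asks whether the intervention-to-control ratio is the same in each subgroup. In a pre/post design, that requires each subgroup's control facilities to supply that subgroup's own background change. The model as described has one background change for everyone.

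For country and size, suppose event rates change between baseline and follow-up by different amounts in Malawi and Uganda, or in large and small facilities, for reasons unrelated to the programme. The exposure-by-subgroup term is then the only term in the fixed part of the model that can represent the difference, so it appears as effect modification.

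Month differs because its main effect is not already in the model. If only an exposure-by-month term is added, intervention facilities may vary by month while control facilities keep one flat post-randomisation level. A season or drift shared by both arms then looks like an effect that grows or fades.

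At stake are statements that the programme works better in one country or type of facility, or that its effect changes over the nine months. The primary effect estimate is not at stake.

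**Working it through.** **The plan's own figures.** The documents give no figure for any subgroup contrast. The design arithmetic reproduces: 1,500 × 23/12 = 2,875 births per facility, and 2,875 × 60 = 172,500 (SAP 16.2). The power statement there concerns the primary contrast and is not in question here.

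**Algebra, country.** Let d1 and d2 be the background pre/post changes in log odds in the two countries, and θ the same treatment effect in both. Control facilities change by d1 and d2; intervention facilities by d1 + θ and d2 + θ. With equal numbers, the common period term estimates (d1 + d2)/2. The exposure effects are then:

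- country 1: θ + (d1 − d2)/2
- country 2: θ + (d2 − d1)/2
- interaction: d2 − d1, when the truth is 0.

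If d1 = d2 there is no bias. With a true odds ratio of 0.75 and d2 − d1 = ln 0.8, the model reports 0.75/√0.8 = 0.84 in country 1 and 0.75 × √0.8 = 0.67 in country 2.

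**Algebra, month (no month effect in controls).** Let g(m) be the shared change in month m and ḡ its nine-month mean. The period term estimates ḡ, so the reported effect in month m is θ + g(m) − ḡ. A shared linear fall of 0.8 from month 1 to month 9 again gives 0.84 and 0.67 when the truth is 0.75 throughout.

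**Simulation inputs.** From the documents: 60 facilities, 30 per country, 1:1; 6 months of baseline and 9 months of follow-up; ICC 0.021 (SAP 16.1); CAC 0.97 (SAP 16.2). Assumed: weekly births of 55/95/140 (Malawi) and 50/72/100 (Uganda), chosen to fall in the size classes of SAP section 12, giving about 333,000 births; event rates guided by the cut points 1.96 and 3.19 in that section, read as percentages; logit-scale variances of 0.58 (facility) and 0.018 (facility-by-period), so 0.58/0.598 = 0.97, with 0.06 as an alternative (0.58/0.64 = 0.91); true odds ratio 0.75 in every subgroup; all trend sizes. The fit was a logistic mixed model with facility-robust standard errors, 250 runs per row. 'Rejected' means p < 0.05 for the interaction, matching "All applicable statistical tests will be two-sided and will be performed using a 5% significance level".

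| Subgroup | Assumed ratio of background change | Interaction only: ratio (rejected) | Time term added: ratio (rejected) |
|---|---|---|---|
| Country | 1.0 | 1.01 (6%) | 1.00 (8%) |
| Country | 0.9 | 0.89 (22%) | 0.99 (6%) |
| Country | 0.8 | 0.81 (61%) | 1.00 (6%) |
| Country | 0.7 | 0.71 (92%) | 1.00 (5%) |
| Size, largest v smallest third | 0.8 | 0.81 (40%) | 1.01 (11%) |
| Month 9 v month 1, linear, shared by both arms | 1.0 | 1.00 (8%) | 1.00 (6%) |
| Month, same | 0.9 | 0.90 (38%) | 1.00 (10%) |
| Month, same | 0.8 | 0.80 (90%) | 0.99 (5%) |
| Month, same | 0.7 | 0.70 (100%) | 1.00 (5%) |

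At the larger facility-by-period variance, country rejection is 14%, 32% and 64% for 0.9, 0.8 and 0.7, and the false ratios are essentially the same. The size test (2 degrees of freedom, uncorrected robust errors) rejects in about 10% of runs even without bias, so 40% should be set against that.

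**Control check.** A strong trend common to all facilities (0.7 over the nine months) left the country ratio at 1.01 (6% rejected) and the size ratios at 1.01 and 0.99 (10% rejected).

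**Month as categories** (60 runs), shared fall of 0.8: the reported odds ratio moved from about 0.84 in month 1 to 0.66 in month 9, in line with the algebra.

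**The case against.** **An interaction is ordinarily fitted with its main effects.** A month main effect in both arms removes the month bias, and the SAP does not say it will be left out. This stands: for month, the documents show an omission to be filled, and a reader who infers that the month analysis must be biased goes beyond them. It does not rescue country and size. Their main effects are already in the model, and a treatment-by-country term does not imply period-by-country.

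**A shared trend is harmless for country and size.** This also stands, as the control check shows. A reader might infer that any secular trend corrupts all three subgroup analyses; for these two, only a trend that differs between subgroups matters.

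**There are safeguards.** SAP 25.2.2.2 plans a graph of outcome rates over time by arm and a table by arm, country and period, and asks for cautious interpretation. These make a misreading less likely, but they do not re-centre a biased estimate or its interval.

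**The trend sizes are invented.** True. The documents give no seasonal, drift or country-trend figure, so no rejection rate above predicts what this trial will show. Rates also vary with the fit: a separate month simulation with no treatment effect and no stated facility-by-period effect rejected in 51% and 99% for drifts of 10% and 20%, against 38% and 90% above. The near one-for-one transfer of a trend into the ratio does not depend on these choices.

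**Sustainability.** One might infer that the month subgroup is the trial's test of sustainability, since SAP 16.1 kept nine months partly for that reason. SAP 16.1 ties it to the implementation and process evaluation, which has its own analysis plan, so the argument adds no weight here.

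**Conclusion.** The concern holds in a limited form. For country and facility size, the model as described attributes any difference in background pre/post change to the treatment effect, almost one for one, and fitting main effects does not prevent this. For month, the specification is incomplete: read literally, shared drift or season becomes a changing effect; with a month effect in both arms it does not.

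How large the error would be depends on trends the documents do not report. Over assumed differences of 10% to 30% between countries, the false ratio of odds ratios is about 0.9 to 0.7. Such differences are plausible: a six-month baseline and a nine-month follow-up need not cover the same seasons, and Protocol 10.1 and 14.2 provide for recording changes in resources and practice. They are not established. The documents therefore do not support saying that the trial will report false effect modification.

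The simulations hold variance components at assumed values, convert ICC and CAC to the logit scale approximately, and use odds ratios, which at event rates near 2% to 3% are close to the planned risk ratios. With 250 runs, rates near 5% are uncertain by about 3 points. The change is worth making before the comparative analysis, but it is not critical to the trial's main conclusion.

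**What to change.** In SAP 25.2.2.2, 'Additional analysis', replace the interaction sentence with text such as:

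*Each subgroup model will include the subgroup main effect, the period-by-subgroup effect and the exposure-by-subgroup effect, where treatment is the exposure indicator of the primary model. For month, the single post-randomisation indicator will be replaced by month indicators applying to both arms, with baseline as reference and months counted from the same anchor in control facilities, plus exposure-by-month.*

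The ratios of ratios are then taken from these models. The anchor can be the one already defined for the line graph, each facility's allocation to the transition phase. No new data are needed: allocation is stratified by country and minimised on size (Protocol 17.2.1), so control facilities should be available in each subgroup to estimate its own change.

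The cost is precision. With s² the variance of a facility's pre/post change and 15 facilities per arm per country, the country interaction variance goes from s²(1/15 + 1/15) = 2s²/15 to 4s²/15, so its standard error rises by √2, about 1.4 times. The size and month contrasts also become less precise; the amount was not calculated.

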25.2.3 Secondary Outcomes

All secondary outcomes are binary and will be analysed using the same methods as the primary outcome. Treatment effects and confidence intervals will be presented, but these outcomes will not be subject to statistical testing.

25.2.3.1 Components of the composite primary outcome

The three components of the composite primary outcome (infection related maternal mortality, infection related maternal near-miss and severe infection related morbidity (deep surgical site infection or body cavity infection), will each be analysed individually using the methods described in section 25.2.2.

25.2.3.2 Stillbirth

25.2.3.2.1 Derivation

Stillbirth is collected on the 'Facilities' database within the instrument named 'Daily Form Area' under the following variables: 'Fresh stillbirths' and 'Macerated stillbirths. These variables are collected daily.

25.2.3.2.2 Analysis

This outcome will be analysed using the methods described in section 25.2.2. The denominator for this outcome will be the sum of all live births and still births.

25.2.3.3 Early neonatal death (infection related and total)

25.2.3.3.1 Derivation

Early neonatal death is collected on the 'Facilities' database within the instrument named 'Daily Form Area' under the following variables: 'Neonatal deaths (inpatients) <28 days after delivery (infection related)' and 'Neonatal deaths (inpatients) <28 days after delivery (not infection-related)'. These variables are collected daily. Total neonatal deaths will be calculated by the summation of the two variables.

25.2.3.3.2 Analysis

This outcome will be analysed using the methods described in section 25.2.2.

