 To examine if the APT-Sepsis programme is effective at reducing individual-level infection related maternal mortality and severe morbidity, and superior compared to usual care with passive guideline dissemination

The secondary objectives are:

- To evaluate if the APT-Sepsis programme is effective at reducing individual level secondary clinical outcomes of: Stillbirth, early neonatal death (infection related and total), maternal mortality (any cause), maternal near miss (any cause)
- To explore differential or subgroup individual-level effects of the APT-Sepsis programme.
- Implementation: To understand the cluster-level implementation of the APT-Sepsis programme in Malawi and Uganda, to facilitate interpretation of trial outcomes and development of a longer-term implementation strategy. A separate analysis plan will be developed for this objective.
- Health economic analysis: To determine if the APT-Sepsis programme is cost effective. A separate analysis plan will be developed for this objective.

9 Study Design

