25.2.3.6.2 Analysis

All implementation outcomes are only measured in the post-intervention period, with each site receiving three visits to assess these outcomes. Analysis will focus on the cluster level, with cluster-level outcomes being calculated as proportions at each of the three visits. Analysis will use mixed-effect

repeated-measures linear regression models to compare APT-Sepsis and Control sites. Country, and the minimisation factor facility size will be included as covariates.

26 Safety Evaluations

The primary and secondary outcomes are all related to safety, and other outcomes. Other safety outcomes, that may potentially be influenced by the intervention, such as caesarean section rates, are presented descriptively as described above in the Facility and Patient characteristics section.

27 Additional Analyses

There are no planned additional analyses. We are not collecting information on individual women who did not experience a severe infection, near-miss or maternal mortality therefore a fully covariate adjusted analysis will not be possible.

28 Document History

Statistical Analysis Plan Version	Protocol Version	Section number(s) changed	Description of changes	Justification for changes	Date Implemented
2.0	Malawi: version 6.0 07/11/2024 Uganda: version 3.0 07/11/2024	25.2.3.4.1	Changed the derivation of the outcome to use the patient database rather than the facility database	The derivation was incorrect, the maternal mortality outcome should be based on deaths recorded in the patient database, rather than summary numbers in the facility database.	04/08/2025

29 References

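### Neonatal death is estimated only among live births and stillbirth separately, so fewer stillbirths could pull the neonatal estimate towards harm, and no planned analysis gives the net effect

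*SAP*

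**What the plan says.** The SAP's secondary objective reads "To evaluate if the APT-Sepsis programme is effective at reducing individual level secondary clinical outcomes of: Stillbirth, early neonatal death", so the programme is expected to act on both outcomes.

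Stillbirth (SAP 25.2.3.2) is counted from the daily facility form, and "The denominator for this outcome will be the sum of all live births and still births".

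Early neonatal death (SAP 25.2.3.3) comes from two fields on the same form. Both count inpatient deaths before 28 days, one infection-related and one not. "Total neonatal deaths will be calculated by the summation of the two variables". For the analysis, "This outcome will be analysed using the methods described in section 25.2.2", with no denominator of its own. In 25.2.2.2, "The denominator for the percentage calculation will be the number of live births recorded in the facility in the time period".

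No outcome in SAP 15.2 or 25.2.3 adds stillbirths and neonatal deaths together, and section 27 says "There are no planned additional analyses". On inference for secondary outcomes, section 25.2.3 says "Treatment effects and confidence intervals will be presented, but these outcomes will not be subject to statistical testing". Section 26 describes the primary and secondary outcomes as all related to safety, and protocol section 16 has the IDMC follow stillbirths and neonatal deaths by arm.

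**The concern.** By the trial's own hypothesis the programme may change how many babies are born alive. If it does, the intervention arm's live births include some babies who would have been stillborn under control. The neonatal comparison is then not a comparison of like groups created by randomisation. The constrained baseline, the random effects and the covariates for country and facility size do not address this, because the selection happens after allocation.

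If the saved babies are frailer than other live-born babies, the neonatal ratio moves upwards although no baby has been harmed. Read alone, or as a safety signal under section 26, that could be taken for harm. The stillbirth result would show the other side of the account, but no planned estimate or confidence interval gives the balance. A combined analysis chosen after the results are seen would be post hoc, which the SAP (section 5) sets out to prevent.

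**Working it through.** The documents give no stillbirth rate, neonatal death rate, expected effect or power for these two outcomes, so there is no plan figure to reproduce. Every input below is an assumption, chosen to show direction and rough size.

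**Inputs (assumed)**
- S = 0.025 stillbirths per birth.
- n = 0.015 inpatient neonatal deaths per live birth.
- a = share of stillbirths averted, 0.10 or 0.20.
- d = share of saved babies who die as inpatients, 0.20 or 0.40.
- g = direct proportional reduction in neonatal deaths among babies who would be live-born anyway, 0, 0.05 or 0.10.

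**Formulas**
- Neonatal RR per live birth = {[n(1−S)(1−g) + d·a·S] / [(1−S) + a·S]} / n.
- Combined RR per birth = [S(1−a) + n(1−S)(1−g) + d·a·S] / [S + n(1−S)].
- The neonatal RR exceeds 1 exactly when a·S·(d−n) > g·n·(1−S). With g = 0 this reduces to d > n: saved babies must be at higher risk than the background.

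**Control arm, per 1,000 births:** 25 stillbirths, 975 live births, 0.015 × 975 = 14.625 neonatal deaths, 39.625 deaths in total.

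**Intervention arm, no direct neonatal benefit (g = 0)**

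| a | d | Live births | Neonatal deaths | Neonatal RR | Total deaths | Combined RR |
|---|---|---|---|---|---|---|
| 0.10 | 0.20 | 977.5 | 15.125 | 1.03 | 37.625 | 0.95 |
| 0.10 | 0.40 | 977.5 | 15.625 | 1.07 | 38.125 | 0.96 |
| 0.20 | 0.20 | 980.0 | 15.625 | 1.06 | 35.625 | 0.90 |
| 0.20 | 0.40 | 980.0 | 16.625 | 1.13 | 36.625 | 0.92 |

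First row in full: 14.625 + 0.2 × 2.5 = 15.125 deaths; 15.125/977.5 = 15.47 per 1,000; 15.47/15 = 1.03. Total: 22.5 + 15.125 = 37.625; 37.625/39.625 = 0.95.

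**With a direct neonatal benefit**
- g = 0.05: neonatal RR 0.98 to 1.08.
- g = 0.10: neonatal RR 0.93 to 1.03; only the corner a = 0.20, d = 0.40 stays above 1.
- Break-even g = a·S·(d−n) / [n(1−S)]. Mildest corner: 0.0025 × 0.185 / 0.014625 = 3.2%. Most extreme corner: 0.005 × 0.385 / 0.014625 = 13.2%.

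**Would total births as denominator cure it?** With g = 0, neonatal deaths over all births give 15.125/14.625 = 1.03 up to 16.625/14.625 = 1.14. They do not. The cause is that the two linked outcomes are analysed apart; the combined count removes the dependence on surviving delivery.

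**The case against.** Five objections deserve weight.

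1. *The averted stillbirth is not hidden.* It is credited in its own outcome, where the scenarios above give RR 0.80–0.90, and a careful reader can set the two results side by side. This stands. What is missing is an estimate and interval for the net effect.

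2. *The size is wholly assumed.* This stands. A programme that also aims to prevent neonatal deaths may well show a neonatal RR below 1, and a direct benefit between about 3% and 13% is enough to remove the reversal in these scenarios.

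3. *The shift would mostly lie within noise, and nothing is tested.* Assume 30 facilities per arm, 80 births a week, 6 months of baseline and 9 of follow-up, 1.5% neonatal death, ICC 0.005–0.021 and CAC 0.97. The 95% interval then extends by a factor of about 1.14–1.20 either side, so even RR 1.13 would include 1 (1.13/1.14 = 0.99). With an ICC of 0.001 or lower the top of the range could exclude 1. These outcomes are exploratory, and section 26 attaches no decision rule. This limits the harm but leaves the estimate hard to interpret.

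4. *The live-birth denominator is stated for a summary percentage.* Its use in the neonatal model follows by cross-reference and is not spelled out. This is fair, and is itself a reason to write it down.

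5. *The combined outcome is imperfect.* It still misses deaths after discharge. True, but the planned neonatal outcome misses them too.

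A reader might go further and infer that staff who know the allocation would classify deaths around delivery differently by arm. The documents show an open-label trial with local data collection. They also say that the data come from routine records, and they show no direction or size of misclassification. A reader might also want fresh stillbirths analysed alone because the form separates them from macerated ones. Neither document says when macerated deaths occur, so that request has no basis here.

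**Conclusion.** The point holds in a limited form. The neonatal estimate is conditional on live birth, an event the programme is meant to influence, and the plan neither says so nor provides a combined estimate. The direction of the pull depends on saved babies having a higher neonatal death risk than other live-born babies. That is plausible but not shown in the documents. Under the assumed rates and no direct neonatal benefit, a neonatal RR of 1.03–1.13 coexists with a combined RR of 0.90–0.96; a direct benefit of 5–10% shrinks or removes the reversal.

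A reader might infer that the neonatal result will show harm if the programme works, or that the live-birth denominator is an error. The documents support neither. The reversal is a possibility, and changing that denominator alone would not prevent it. The primary outcome and its model are untouched. This is a cheap improvement to the exploratory outcomes.

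**What to change.** In SAP 25.2.3 add one exploratory secondary outcome: (stillbirths + inpatient neonatal deaths before 28 days) / (live births + stillbirths), fitted with the 25.2.2.2 model and reported beside the two separate outcomes. In 25.2.3.3.2 state that the neonatal analysis uses live births as its denominator and that its estimate is conditional on live birth.

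The cost is a few lines of SAP text and one more model on counts already recorded on the daily facility form; no new data are needed. The downside is one more exploratory estimate, unadjusted for multiplicity like the others. Describing it as stillbirth plus inpatient neonatal death makes clear that later deaths are not captured.
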